1.1 Research Background

Football, as the most popular sport in the world, requires high athletic capacity. During a 90-minutes match, athletes must repeatedly perform high-intensity actions like prolonged running, sprints and decelerations (Jimenez-Iglesias et al., 2024). Simultaneously, they must execute technical skills like dribbling and passing under fatigue, which shows the need of training methods develop not only conditioning but also technical skills for players. However, conventional training programs often fail to combine these components efficiently, resulting in limited transfer to match performance (Akdoğan et al., 2021). This gap is vital during puberty — a key developmental period for a youth soccer player, in which athletes gain dramatically in strength, speed, endurance and skills under the scientific conditioning (Badenhorst, 2017; McBurnie et al., 2021). Therefore, it is crucial to find training strategies that can enhance both physical capacities and sport-specific skills.

Small-sided games (SSGs) seem to be a potential solution for integrating fitness and technical skills, has been widely used by soccer coaches during the last decade. SSGs require players execute passing, dribbling and shooting by simulating dynamic match in smaller pitches, thereby enhancing technical skills and maintaining physical capacities (Badenhorst, 2017; F. M. Clemente et al., 2023). Furthermore, their game-based design might be more attractive and enjoyable than traditional protocols for adolescents (Los Arcos et al., 2015). Despite of these advantages, SSGs may prioritize technical skills and anaerobic fitness like explosive power and agility over aerobic fitness (Thapa et al., 2023; Wen et al., 2024). Current evidence seems controversial: some researches demonstrated comparable endurance improvements between SSGs and traditional training, others suggest better promotion from

conventional aerobic training (Eniseler et al., 2017; Jastrzebski et al., 2014; Moran et al., 2019). Thus, the effectiveness of SSG in enhancing aerobic fitness requires further examination, and a more comprehensive training protocol should be developed.

To address the technical and physical deficit in SSGs and conventional conditioning, we develop a new sport-specific protocol: Yo-Yo with Ball Training. The original Yo-Yo Intermittent Recovery 1 (Yo-Yo IR1) was primarily designed to assess repeated sprint ability, has been demonstrated strong correlations with soccer athletes' aerobic and anaerobic capacities (Grgic et al., 2019). Moreover, when implementing this 40m increasing speed shuttle run as a high-intensity interval training (HIIT) tool, it could greatly improve individuals' aerobic and anaerobic performance (Delahunt et al., 2013).

However, traditional Yo-Yo protocol lacks the combination of physical and technical stimuli. While simulating real-match movements, like shuttle run involving acceleration, deceleration and 180° turns, they neglect ball-control skills, like dribbling and shielding, a critical factor of selecting talented and predicting match performance (Fuhre et al., 2022; Haroune et al., 2024). Crucially, previous research indicates that dribbling combined with interval training boost both aerobic capacity and anaerobic power (McMillan et al., 2005). By integrating ball dribbling into each shuttle run phase, the modified Yo-Yo protocol could enhance explosive power, physical endurance, change of direction and the stability of dribbling of youth soccer players simultaneously. This approach may not only promote physical capacities but also trains sport-specific skills. Considering this area lacks research, the further investigation is required.

1.2 Purpose of the Study

This study aims to investigate the differential effects of three training protocols:

traditional Yo-Yo intermittent training, ball-dribbled Yo-Yo intermittent training, and small-sided games (SSGs) on aerobic capacity, anaerobic and soccer-specific performance in adolescent soccer players following a 4-week intervention.

1.3 Research Questions of the Study

Q1: How do 4-week interventions of traditional Yo-Yo training, ball-dribble integrated Yo-Yo training, and small-sided games (SSGs) influence aerobic capacity in adolescent soccer players?

Q2: How do 4-week interventions of traditional Yo-Yo training, ball-dribble integrated Yo-Yo training, and small-sided games (SSGs) influence anaerobic performance in adolescent soccer players?

Q3: Are there between-group differences in the improvements across aerobic, capacities?

Q4: Are there between-group differences in the improvements across anaerobic capacities?

1.4 Hypothesis of the Study

H1: The aerobic capacity of adolescent soccer players will improve following a 4-week intervention.

H2: The anaerobic performance of adolescent soccer players will improve following a 4-week intervention.

H3: Aerobic adaptations will be equivalent between traditional Yo-Yo and ball-dribble Yo-Yo groups, with both superior to SSGs.

H4: Anaerobic performance will be equivalent between ball-dribble Yo-Yo and SSGs groups, with both superior to traditional Yo-Yo.

Chapter 2 Literature Review

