3.1 Participants

Participants should be recruited from middle school soccer teams. Participants shall fulfill all the following inclusion criteria to be included in the study: (1) be aged between 13 and 18 years; (2) have received at least one year of formal football training; (3) have no history of major sports-related injuries; (4) be in good general health, without smoking or alcohol consumption habits; and (5) have no known psychological or psychiatric disorders that may affect participation; (6) have not participated in any similar intervention within the past year; (7) attend the training sessions regularly. Participants should be excluded according to the following criteria: 1. are outside the age range of 13–18 years; 2. have less than one year of formal football training experience; 3. have a history of major sports-related injuries; 4. have chronic diseases or unhealthy habits such as smoking or alcohol consumption; 5. have known psychological or psychiatric disorders that may affect participation; 6. have participated in similar training interventions within the past year; 7. fail to attend at least 75% of the 12 training sessions.

The required sample size was calculated using G*Power 3.1 software based on a repeated-measures ANOVA (within-between interaction). The average effect size (f) was set at 0.25 (Cherni et al., 2025; Li et al., 2022), with a significance level of 0.05, and the desired statistical power of 0.80 achieved. The calculations indicated that a minimum of 42 participants are required in total, considering the 20% dropout, at least 50 participants should be recruited at the screening session.

The experimental procedures will be explained to participants and their parents at the screening-baseline. Before data collection, the written informed consent should also be provided. During the study, the participants will all attend regular schools and

football trainings. This research should receive approval from the Ethics Committee of University of Macau.

[figure not shown]

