3.5 Statistical Analysis

Data analysis will be conducted using SPSS 29.0. First, descriptive statistics will be performed to summarize sample characteristics. Independent samples t-tests will be used to compare baseline differences between groups. The Shapiro-Wilk test will be applied to assess normality; if data violate normality assumptions, appropriate adjustments will be implemented.

A two-way repeated measures ANOVA (group \times time) will be utilized to examine between-group effects, time effects, and interaction effects on outcomes including aerobic and anaerobic performance. If significant interactions are detected, Bonferroni post-hoc tests will be conducted to identify simple main effects.

Effect sizes will be reported as partial eta-squared (η^2) for ANOVA results, with $\eta^2 < 0.06$ considered small, 0.06-0.14 moderate, and >0.14 large. Within-group effect sizes will be calculated using Cohen's d, where $d = 0.2$, 0.5 , and 0.8 represent small, medium, and large effects, respectively. Statistical significance is set at $\alpha = 0.05$, and results will be presented as mean \pm standard deviation (Mean \pm SD).

References

- Akdoğan, E., Yılmaz, İ., Köklü, Y., Alemdaroğlu, U., & Cerrah, A. O. (2021). The effect of isolated or combined small-sided games and speed endurance training on physical performance parameters in young soccer players. *Kinesiology*, 53(1), 78–85. <https://doi.org/10.26582/k.53.1.10>
- Badenhorst, J. (2017). *The effect of the growth spurt on strength, power, speed and agility training in boys during mid-adolescence* [PhD Thesis, North-West University (South Africa), Potchefstroom Campus]. <https://repository.nwu.ac.za/handle/10394/30657>
- Clemente, F. M., Praça, G. M., Aquino, R., Castillo, D., Raya-González, J., Rico-González, M., Afonso, J., Sarmiento, H., Silva, A. F., Silva, R., & Ramirez-Campillo, R. (2023). Effects of pitch size on soccer players' physiological, physical, technical, and tactical responses during small-sided games: A meta-analytical comparison. *Biology of Sport*, 40(1), 111–147. <https://doi.org/10.5114/biolsport.2023.110748>

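### H3 and H4 each predict that one pair of arms is equivalent, but section 3.5 plans only difference tests, so no planned result can validly support those clauses

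*Combined protocol and SAP*

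**What the plan says.** Section 1.4 gives two between-group hypotheses, each with an equivalence clause and a superiority clause:

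- The aerobic hypothesis (H3) reads "Aerobic adaptations will be equivalent between traditional Yo-Yo and ball-dribble Yo-Yo groups, with both superior to SSGs". The pair claimed to be alike is the two Yo-Yo arms.
- The anaerobic hypothesis (H4) pairs the arms differently: "Anaerobic performance will be equivalent between ball-dribble Yo-Yo and SSGs groups, with both superior to traditional Yo-Yo".

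Section 3.5 plans a two-way repeated-measures ANOVA that "will be utilized to examine between-group effects, time effects, and interaction effects on outcomes including aerobic and anaerobic performance". Pairwise comparisons are conditional: "If significant interactions are detected, Bonferroni post-hoc tests will be conducted to identify simple main effects". The effect sizes to be reported are partial eta-squared for the ANOVA and Cohen's d within groups. Neither measures the difference between two named arms.

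Section 3.1 sizes the trial for the group-by-time interaction, with alpha 0.05 and power 0.80. On the effect it says "The average effect size (f) was set at 0.25". The result is a minimum of 42 players in total, with at least 50 to be recruited.

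The text gives no equivalence margin, no equivalence test, no between-arm confidence interval, and no statement of what result would support an equivalence clause.

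**The concern.** Equivalence is a positive claim: the true difference is smaller than some stated amount. A difference test cannot establish it, because a non-significant result arises either from similar arms or from too few players to tell them apart. Here the planned tests bear on the equivalence clauses only through non-significance. The smaller the sample and the stricter the multiplicity correction, the more readily that result appears. If the interaction is not significant, the named pairs are not compared at all.

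At stake are two conclusions: that adding the ball costs no aerobic gain, and that the ball-dribbled protocol matches SSGs on anaerobic performance. As planned, each clause is either left untested or open to support from a result that cannot bear the weight.

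**Working it through.** **Inputs from the documents.** Three groups and two time points (section 3.2); f = 0.25, alpha 0.05, power 0.80, minimum N = 42, at least 50 recruited, 20% dropout (section 3.1).

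**Assumptions.** The documents do not state the pre-post correlation (rho), the allocation ratio or a margin. I take rho = 0.5, 1:1:1 allocation and a range of margins. Section 3.2 also speaks of four groups in places; three is used here because three are named and three reproduce the sample size.

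**Step 1: reproduce the plan's N.**
- Noncentrality = f² × N × m / (1 − rho) = 0.0625 × 42 × 2 / 0.5 = 10.5, with 2 and 39 degrees of freedom. Power = 0.803, so N = 42 is reproduced.
- Other inputs do not give 42: rho 0.3 gives 60, rho 0.7 gives 27, and four groups at rho 0.5 give 48.
- Equal allocation gives 42 / 3 = 14 per arm.

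**Step 2: what difference that N targets.**
- As a one-way comparison of change scores, the effect size is √(10.5 / 42) = 0.5.
- For two equal arms and one lower by δ, the effect size is δ√2 / 3, so δ = 0.5 × 3 / √2 = 1.06 SD of change.

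**Step 3: how often one pairwise difference test is non-significant.** The standard error is √(2/14) = 0.378 SD of change, with 39 degrees of freedom. The test is two-sided and taken by itself, without the interaction gate.

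| True difference (SD of change) | Unadjusted | Bonferroni, 3 pairs |
|---|---|---|
| 0.5 | 75% | 87% |
| 0.8 | 46% | 64% |
| 1.06 | 22% | 38% |

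For 0.5 SD, 13 per arm (50 × 0.8 = 40 completers) gives 76% and 88%; 16 per arm gives 72% and 85%.

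**Step 4: what an equivalence test could show at this size.**
- The 90% confidence interval half-width is t(0.95, 39) × 0.378 = 1.685 × 0.378 = 0.64 SD of change. A margin below that can rarely be met.
- Power of two one-sided tests at 0.05, with a true difference of zero:

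| Margin (SD of change) | Power |
|---|---|
| 0.5 | 0.2% |
| 0.8 | 34% |
| 1.0 | 66% |
| 1.13 | 80% |

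- Using only the two arms' own variance, 80% power needs 70 per arm for a 0.5 SD margin and 28 per arm for 0.8 SD.
- The margin needed for 80% power at 14 per arm (1.13 SD) exceeds the 1.06 SD difference that the trial is sized to detect.

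**The case against.** A reader might infer that the plan will declare arms equivalent whenever p > 0.05, and that a materially worse arm would usually pass as equivalent. The documents do not support that.

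- **No such rule is written.** The plan does not say what result would count as equivalence. Reading non-significance that way is an inference, although no other planned result bears on the clause.
- **The 87% is not the probability of falsely supporting H3.** It is for one pair, ungated. The plan requires a significant interaction first, and H3 also needs both Yo-Yo arms to beat SSGs. Simulating that whole sequence (14 per arm, ball-dribbled arm truly 0.5 SD below traditional, Bonferroni over three pairs) gives apparent support for all of H3 about 0.5% of the time if SSGs equal the ball-dribbled arm. The figure is roughly 14 to 15% if SSGs lie 1.06 SD below traditional, and 56% if SSGs lie a further 1.06 SD below the ball-dribbled arm. The answer depends on where SSGs sit.
- **The 0.5 SD is illustrative.** The documents name no important difference for any outcome. At 1.06 SD the Bonferroni test misses only 38%.
- **The Bonferroni family is assumed.** Section 3.5 does not say whether the simple main effects compare groups at each time or times within each group.
- **Equivalence is not the study's stated purpose.** Section 1.2 asks about differential effects, and Q3 and Q4 in section 1.3 ask about between-group differences, which the ANOVA addresses.

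All of this stands and limits the claim. It does not supply a valid route to the equivalence clauses.

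**Conclusion.** The concern holds in a limited form: the equivalence clauses of H3 and H4 have no decision rule and no planned analysis that can validly support them. The superiority clauses, H1 and H2 are not touched by this defect.

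The exact percentages rest on three equal arms at the minimum N. In units of SD of change, Steps 3 and 4 depend on the number per arm; rho = 0.5 enters through reproducing N = 42 and the 1.06 SD conversion. The 13 and 16 per arm checks move the figures by a few points and leave the conclusion unchanged. A formal equivalence test at this size has little power unless the margin is about 1.1 SD of change or wider, so adding one without changing the claim would mostly yield inconclusive results.

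**What to change.** **Recommended.**
1. In section 1.4, replace the equivalence wording in H3 and H4 with, for example, 'no large difference expected; difference to be estimated'.
2. In section 3.5, report the between-arm difference in change with a 95% confidence interval for traditional versus ball-dribbled Yo-Yo (aerobic) and ball-dribbled Yo-Yo versus SSGs (anaerobic), whether or not the interaction is significant.
3. State in section 3.5 that p > 0.05 will not be read as equivalence.

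**If the sponsor keeps an equivalence claim.** Before the data are seen, specify and justify a margin in raw units for each outcome concerned. Conclude equivalence only if the 90% confidence interval lies wholly inside the margin; otherwise report the result as inconclusive. Acknowledge that power is low for any margin well below about 1.1 SD of change.

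**Cost.** The recommended change is a wording edit in two sections plus a confidence interval for the named pair on each relevant outcome. It needs no extra players, visits or measurements. The price is more modest claims.

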2.1 The Athletic Demands of Soccer Player

Modern soccer demands that players perform frequent high-intensity efforts—such as sprinting, turning, and rapid accelerations—interspersed with periods of lower-intensity activity. These actions vary according to match context and playing position. For instance, midfielders and wide attackers typically perform more high-speed runs than defenders or goalkeepers (Jerome et al., 2024; Sarmento et al., 2024). Although most existing studies focus on adult athletes, similar positional differences are observable in youth soccer players (Gil et al., 2007).

Adolescence is a period of rapid physical development. During puberty, boys experience substantial gains in height, strength, aerobic capacity, and muscular coordination. However, these gains do not occur uniformly and may temporarily disrupt motor control, increasing injury risk (Ribeiro et al., 2024). Therefore, the design of youth training programs must account for both the physiological demands of soccer and the biological variability among athletes.

2.2 Effects of Small-sided Games on Athletic Performance

Small-sided games (SSGs) have become a widely adopted training method in soccer, due to their ability to integrate physical, tactical, and technical demands in a game-representative environment (Halouani et al., 2014). Played on reduced pitch sizes with fewer players, SSGs simulate match situations that require frequent decision-making, ball-handling, and high-intensity efforts over short bursts, making them an effective method for improving agility, speed, and anaerobic power (F. Clemente et al., 2022; Thapa et al., 2023).

Recent randomized controlled trials have provided strong evidence of their efficiency. A study showed that six weeks of 4v4 SSG training produced

significant improvements in VO₂ max and CMJ height in adolescent players, superior to traditional interval running protocols (Los Arcos et al., 2015). Similarly, a large-scale meta-analysis confirmed that SSGs can match the effects of traditional continuous running on aerobic performance, especially when game formats are properly structured to maintain high intensity (Moran et al., 2019).

However, the effectiveness of SSGs on aerobic development can vary depending on design variables such as pitch size, player numbers, and rest ratios. Research noted that these parameters must be carefully manipulated to ensure the physiological demands are sufficient for aerobic adaptation (Cherni et al., 2025).

In summary, SSGs is a powerful training tool for youth soccer, capable of simultaneously developing physical fitness and sport-specific skills. However, to optimize outcomes—particularly in aerobic conditioning—coaches should adjust SSG variables according to the developmental needs of the players and the targeted physical qualities.

2.3 Effects of Yo-Yo Intermittent Recovery on Athletic Performance

The Yo-Yo Intermittent Recovery Test Level 1 (Yo-Yo IR1) is one of the most widely used tools for assessing and developing soccer-specific endurance (Grgic et al., 2019). Designed to mimic the stop-start demands of competitive play, Yo-Yo IR1 consists of progressively faster shuttle runs interspersed with brief recovery periods, making it suitable for not only evaluation but also high-intensity interval training (HIIT). Studies have indicated its effectiveness in improving both aerobic and anaerobic capacities (Delahunt et al., 2013). However, despite its strong physiological basis, the use of Yo-Yo IR1 as a systematic training intervention remains relatively rare in empirical research.

High-intensity interval training (HIIT), on the other hand, has been extensively studied and validated as a highly effective approach to enhance endurance and

repeated sprint ability in soccer players. Meta-analyses have consistently shown that HIIT interventions produce significant improvements in VO_2 max, lactate threshold, and anaerobic performance in both youth and adult soccer populations, often outperforming moderate-intensity continuous training (Manuel Clemente et al., 2021).

Given that the Yo-Yo IR1 protocol is structurally a standardized shuttle-based HIIT format, its physiological effects can be reasonably inferred from the broader HIIT literature. The repeated accelerations, decelerations, and recovery intervals inherent to Yo-Yo IR1 align with the principles of effective HIIT, supporting its use as a time-efficient and sport-specific conditioning method. This provides a strong rationale for its inclusion in youth soccer training programs, even in the absence of extensive Yo-Yo-specific intervention trials.

Despite these benefits, traditional Yo-Yo protocols lack technical integration. The running patterns simulate match movement, but they do not include ball-handling or decision-making elements, which are essential to match performance. Emerging research highlights that integrating technical actions into physical training can lead to greater improvements in game-relevant performance variables, such as dribbling stability and reactive agility (Eraslan et al., 2025; Sun et al., 2022).

To address this research gap, ball-dribbled Yo-Yo intermittent training becomes a potential solution. Though lack of investigation, related research supports the idea that combining technical skills with interval training can enhance both anaerobic power and technical execution (Karahan, 2012).

2.4 Summary

This chapter has reviewed the athletic demands of adolescent soccer players and the effects of various training interventions. Youth players' athletic performance

depends on a balance of aerobic endurance, anaerobic power, and technical proficiency, all of which undergo significant development during adolescence. Small-sided games could enhance technical and anaerobic qualities, though their aerobic impact may vary depending on format and intensity. Conversely, the Yo-Yo Intermittent Recovery protocol demonstrates strong potential for improving endurance through high-intensity interval training, but it lacks integration of sport-specific technical skills.

To bridge the gap between physical conditioning and technical development, emerging modifications such as incorporating ball-dribbling into interval-based training have been suggested. This approach may offer a more holistic training stimulus by simultaneously targeting aerobic, anaerobic, and technical domains. However, further research is needed to evaluate the effectiveness and practicality of such hybrid protocols, particularly in youth development contexts.

Chapter 3 Research Methodology

